Real-time assessment of pain and mobility. At some point during the baseline sessions, participants may be trained by study staff in the use of the Samsung Gear S[®] or Apple smartwatch or Oura Ring. Participants will also be given a guidebook explaining how to use the smartwatch/ring. Traditional self-report measures of pain cannot capture real-time data under naturalistic conditions or measure fluctuations on a daily or hourly basis. The UF Institute of Aging Data Science and Applied Technology (**DSAT**) Core has recently validated the use of electronic data capture by the Samsung Gear S[®] or Apple smartwatch to measure pain, mood, mobility, and other outcomes in older adults.^{92,93} The DSAT Core infrastructure includes a secure smart watch app which summarizes sensor-monitored data (e.g., tri-axial accelerometer, GPS location) and a graphical interface allowing ecological momentary pain, mood and social activity assessments through a turn dial bezel (**Figure 8**). Data collection on smart watches offers several advantages

including capability of long-term continuous data collection, ecological validity, cost effectiveness, and convenience and low participant burden. “Momentary” pain intensity will be captured randomly four times per day throughout the study. Data will be downloaded remotely or when the individual reports to the clinic during the intervention phase. Participants will start wearing the device during the baseline weeks and at each visit their proficiency and use will be ascertained. Data extraction and analysis will be performed by the DSAT Core.

Figure 8. (a) The Samsung Gear S smartwatch is used by rotating the bezel to select pain ratings; (b & c) the color schema changes from green to reddish-orange as ratings are elevated toward 10; (d) ratings are then saved by pressing a physical, top-right hand button located on top of the bezel.

[figure not shown]
Sensory Assessment Visits (Pre/Post)

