4) Sleep and Food Recall: Self-reported sleep quality during the past month will be measured using the Pittsburgh Sleep Quality Index (**PSQI**).¹⁰⁰ We will also ask participants to report what they ate the previous 24 hours. **5) Interoceptive awareness:** We will assess self-reported interoceptive awareness using the multidimensional assessment of interoceptive awareness (MAIA)¹¹⁴ **6) Chronic Stress:** Using the **Daily Stress Inventory**, we will collect participants' self-reported daily assessment of the sources and individualized impact of relatively minor stressful events.¹¹⁵ **7) Perceived Stress Scale:** Participants fill out a self-report assessment of their thoughts and feelings during the last month.¹¹⁶ **8) Impulsivity:** We will assess self-reported behavioral inhibition using the Behavioral Inhibition System and Behavioral Activation System (BIS/BAS) scales.¹¹⁷ **9) Neuropathy:** Individuals will respond to the PainDetect questionnaire to assess neuropathic pain detection. If an individual scores greater than 12, their clinical pain for each area of testing will be assessed during the

Figure 9. Sensory assessment session protocol

quantitative sensory testing session.¹¹⁸ **10) Empathy:** We will assess empathy using the Affective and Cognitive Measure of Empathy (ACME) questionnaire.¹¹⁹ **11) Back Pain:** If an individual indicates they experience back pain, we will assess such pain using the Chronic Low-Back Pain (Minimal Dataset)¹²⁰, Oswestry Low Back Pain Disability Questionnaire¹²¹, and Brief Pain Inventory¹²² questionnaires. **12) Early Trauma:** Individuals will respond to the Childhood trauma questionnaire-short form (CTQ-SF)¹²³, the Adverse and Traumatic Experiences Scale¹²⁴ and the Brief Resilient Coping Scale.¹²⁵ **13) Aggression:** Individuals will respond to the State-trait Anger Expression Inventory-2 (STAXI-2)¹²⁶, Cohen-Mansfield Agitation Inventory (CMAI) aggressive behavior subscale (CMAI-ABS)¹²⁷ and the Ryden Aggression Scale (RAS) physically aggressive behavior subscale (RAS-PABS)¹²⁷.

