(e.g., for osmolality levels, sodium levels, and any other blood markers out of range) to ensure that no adverse changes have occurred during the study intervention. Additionally, before and after the intervention period participant will fill out the Goal Attainment Scale (**GAS**). For the majority of the 4-week intervention periods, participants may complete daily assessments via their Samsung Gear S® or Apple smartwatch or Oura Ring. We will be able to assess pain, mood, and activities at random times throughout the day. Participants will be contacted once a week to assess side effects and asked if they have been completing their diaries. Any symptom reported as moderate or severe will be brought to the PIs' attention and will be discussed with the study MD as needed on a case by case basis. These weekly calls will also ensure regimen compliance and will assist participants in download of the Samsung Gear S® or Apple smartwatch or Oura Ring data to a secure research server. We have successfully established a similar approach in other projects within our institute, and the DSAT Core has validated pipelines for data analysis.^{92,106}

Post-Intervention Assessments for Knee OA Participants

In the last week of the intervention, participants will be scheduled to return for up to four (or 6 with the MRI) post-intervention visits, which will be identical (with minor exceptions) to the baseline visits. Importantly, at the follow-up Health Assessment we will assess changes in health status, and their global impression of change (**PGIC/MPIC**) since starting the intervention.

Wash-out Period for Knee OA Participants

Participants will undergo a four-week wash-out period in between phases one and two. The wash-out period will serve to prevent confounding variables between both drug administrations. Four weeks is a sufficient period of time for participants to return to baseline levels prior to drug administration.

Phase Two Procedures for Knee OA Participants

After the four-week wash-out period, participants will enter phase two of the study. Phase Two is completely identical to Phase One: up to 4 (or 6 with the MRI) Baseline Visits, Intervention Period, and up to 4 (or 6 with the MRI) Post-Intervention Visits. Participants will be given the other drug from the first intervention period per randomization.

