
Rigor of the prior research. There are noted gaps and weaknesses of the prior research that need to be addressed in order to move this field forward that this application plans to address. Historically, the consideration of pain impact has been overlooked, likely leading to inconsistent results among the literature observing the

relationship between AD/ADRD and chronic pain. Additionally, studies implicating lifestyle factors such as nutrition as a possible mechanism influencing the relationship between pain and cognitive disease have not been completed, despite evidence of nutrition status influencing on both disease states independently. Finally, the examination of epigenetics (influenced by nutrition) such as DNA methylation and epigenetic/cellular aging as a common mechanism driving both pain and AD/ADRD in tandem has not been appreciated. This proposal not only will provide the candidate with the opportunity to train in an outstanding research environment, but also allow her to contribute to filling the gaps in the literature that will allow the field to progress towards solutions to solve the complex problems seen in chronic pain and AD/ADRD.

5. Specific Aims

Specific Aim 1: Determine the association among DII, epigenetic clocks/cellular aging and cognitive function middle-age and older adults with low-impact pain, high-impact pain and pain free controls.

Hypotheses 1a-d: Individuals with chronic pain will (H1a) have a more positive/inflammatory DII, which will be associated with (H1b) accelerated epigenetic aging and (H1c) greater cognitive impairment. These associations will be more significant in the high-impact pain group compared to those with (H1d) low-impact pain and pain-free controls.

6. Research Plan

We propose a cross-sectional, observational study design that will assess the relationship between pain, cognition and dietary pattern in older adults with and without symptomatic knee OA pain. This will be completed in 2 experimental sessions approximately one week apart. After initial screening, eligible participants will undergo the sessions (health and sensory sessions) for collection of clinical, functional (physical, cognitive, emotional), QST, and blood-based biomarker data lasting 2-3 hours.

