Dietary Inflammatory Index. The Dietary Inflammatory Index (DII) was developed to provide a quantitative means for assessing the role of diet in relation to health outcomes ranging from blood concentrations of inflammatory cytokines to chronic diseases. **For the K99 phase**, diet data has been previously collected in the form of a 24-hour food recall. To collect diet data, participants were asked to document food and beverages consumed, as well as supplements taken 24 hours prior to their visit. Assessments were conducted interview-style by a trained research assistant in order to probe deeper into the details of meals. Visual aids such as standard measuring cups, plates, and drink cups in various sizes etc. were provided to aid in accuracy. These data will then be entered into the Nutrition Data System for Research (NDSR) for nutrient analysis. Following quantification, nutrient values will be used to calculate DII score according to the instructions laid out by Hebert & Shivappa et al⁶⁵.

Vitamin A and D Analyses. In order to quantify serum Vitamin D levels, the Quantikine[®] Human Vitamin D BP immunoassay (R&D Systems) will be employed. To quantify Vitamin A levels, a Colormetric Human Vitamin A ELISA Kit (Novus Biologicals) will be used. Kit-specific protocols will be used during quantification.

Epigenetic Analyses. Details regarding the protocol for processing and analyzing epigenetic data published elsewhere^{66, 67}. In short, the raw data generated by Illumina EPIC array (.idat files) will undergo quality control and normalization prior to the calculation of DNAmGrimAge via an online calculator (dnamage.genetics.ucla.edu). The age-adjusted AgeAccelGrim variable will be calculated as the difference between chronological age and DNAmGrimAge and used throughout the analyses.

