Hypotheses and data-analytic strategy: Prior to the testing of proposed hypotheses, each variable will be carefully examined to identify missing values, statistical outliers, and violations of relevant assumptions (i.e., Durbin-Watson, Shapiro-Wilk). Sensitivity analyses would then be completed to examine differences in results between variables with missing data and those same variables with data imputation. A corrected threshold will be set to 0.05, two-tailed. Descriptive statistics will be computed and represented as percentages or means (standard deviations). Group differences (pain impact groups; Vitamin A and D clinical cutoff differences) among potential covariates of interest will be examined using a series of one-way analysis of variance tests (ANOVAs) with follow-up/post hoc Bonferroni corrections. All participants will be matched on race and sex due to their relationships with pain and cognitive outcomes. All statistical analyses employed in this study were performed using SPSS (IBM) version 28.0 (IBM; Armonk, NY). Specific to hypotheses 1a-d: Sequential hierarchical multiple regression models will be employed to investigate the extent to which the continuous DII variable is associated with (H1a) greater severity, duration, and frequency of experimental and clinical pain outcomes, (H1b) accelerated epigenetic aging, and (H1c) worse cognitive decline between individuals with and without pain. Analyses of Variance (ANOVAs) will be performed in order to examine differences in variables of interest between groups: high-impact chronic pain, low-impact pain, and pain free controls. Additionally, three separate sequential hierarchical regression models within each group will be used to examine the extent to which higher scores DII scores are associated with epigenetic aging and cognitive outcomes. Variables of interest (DII, epigenetic age, cognitive status) will be entered into *step 1* of the analysis, relevant clinical covariates (e.g., BMI, smoking) will be entered in *step 2* of the hierarchical regression models, and relevant demographic variables (i.e., age, race, sex, etc.) in *step 3* of the regression models. Finally, a modified Poisson-regression analysis will be performed to assess the relative risk of clinical cognitive impairment between pain impact groups.

7. Possible Discomforts and Risks

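### PANDA's diet exposure rests on a 24-hour recall with no averaging or measurement-error correction, which attenuates the DII regressions; a second recall fits sessions already scheduled

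*Combined protocol and SAP*

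**What the plan says.** **Source of the exposure.** PANDA section 6, Dietary Inflammatory Index, states that "diet data has been previously collected in the form of a 24-hour food recall". Participants listed food and drink "as well as supplements taken 24 hours prior to their visit", in an interview with visual aids; nutrient values then give the DII score. The text names one recall and one visit. It gives no number of recalls and no rule for combining them.

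**Role in the analysis.** PANDA section 6, Hypotheses and data-analytic strategy: "Sequential hierarchical multiple regression models will be employed to investigate the extent to which the continuous DII variable is associated with" pain outcomes (H1a), epigenetic aging (H1b) and cognition (H1c). Further regressions on DII are run within each of the three pain-impact groups, and ANOVAs compare the groups. The only sensitivity analysis described concerns missing data.

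**Opportunities for repeats.** In the parent UCOPE protocol, section 6, item 4 of the questionnaire list for the sensory visits reads "We will also ask participants to report what they ate the previous 24 hours". Those visits are held before and after treatment. The plan has "post-intervention visits, which will be identical (with minor exceptions) to the baseline visits", and Phase Two repeats Phase One. Of PANDA itself, the Research Plan says: "This will be completed in 2 experimental sessions approximately one week apart". PANDA's own sensory-visit list has a sleep item but no food recall, and no prospective diet procedure is written for the 40 new participants.

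**The concern.** PANDA's stated goal concerns overall diet pattern, and its outcomes (chronic pain, epigenetic aging, cognition) develop slowly. The exposure that matters is usual diet. One day's intake equals usual intake plus random day-to-day variation, and ordinary regression treats the resulting score as if it were measured without error.

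Where DII is the predictor, this shrinks its coefficient and lowers power. A null DII result could then reflect either no association or a noisy exposure, and the plan contains nothing that would separate the two. Elsewhere the plan does replicate noisy measures: pressure pain thresholds are averaged over three trials, and the parent study's immune assays are run in triplicate. The main exposure has no such provision.

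**Working it through.** **The plan's own figures.** 50 stored + 40 new = 90, as stated. The 90 is said to include 20% attrition, and 90 × 0.8 = 72. PANDA gives no effect size, standard deviation or target power, so the power basis cannot be reproduced.

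**Inputs**
- From the documents: n = 90 (72 after attrition); two-sided 0.05; three groups of unstated size.
- Assumed: true correlation between usual DII and outcome ρ = 0.30 or 0.35; one-day reliability R = 0.25, 0.50 or 0.70; about 30 people per group.

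**Formulas** (classical error, unrelated to the outcome)
- Reliability of the mean of k recalls: R_k = kR / (1 + (k − 1)R).
- A simple regression slope is multiplied by R_k; the observed correlation is r = ρ√R_k.
- Power = Φ(atanh(r) × √(n − 3) − 1.96), with √87 = 9.33 at n = 90.

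Worked case, ρ = 0.35 and R = 0.25:
- One recall: r = 0.35 × 0.5 = 0.175; atanh = 0.1768; 0.1768 × 9.33 − 1.96 = −0.31; power 0.38.
- Two recalls: R_2 = 0.50/1.25 = 0.40; r = 0.35 × 0.632 = 0.221; atanh = 0.2251; 0.2251 × 9.33 − 1.96 = 0.14; power 0.56.

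**Results at n = 90**

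| R | slope factor, 1 → 2 recalls | power at ρ = 0.30, 1 → 2 recalls | power at ρ = 0.35, 1 → 2 recalls |
|---|---|---|---|
| 0.25 | 0.25 → 0.40 | 0.29 → 0.43 | 0.38 → 0.56 |
| 0.50 | 0.50 → 0.67 | 0.52 → 0.65 | 0.65 → 0.78 |
| 0.70 | 0.70 → 0.82 | 0.67 → 0.74 | 0.80 → 0.87 |
| no error | 1 | 0.82 | 0.93 |

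At n = 72 the range over the same assumptions is 0.24 to 0.71 with one recall and 0.36 to 0.78 with two, against 0.73 to 0.86 without error. In a group of about 30, one-recall power is 0.12 to 0.35, against 0.36 to 0.48 without error, so the within-group models are weak even with a perfect exposure.

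**Covariates.** Adjustment deepens the attenuation if covariates explain part of usual diet. If they explain 20% of it (assumed), the slope factor at R = 0.50 is 0.8/(0.8 + 1) = 0.44 rather than 0.50 with one recall, and 0.8/(0.8 + 0.5) = 0.62 rather than 0.67 with two.

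**Where the bias does not apply.** With DII as the outcome, as in the ANOVA across pain groups and in H1a as worded in the Specific Aims, random error widens the spread but leaves the mean difference unbiased. Vitamins A and D are assayed in serum and do not depend on the recall.

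**The case against.** **Only one recall is used.** A reader might infer this as a stated decision. The PANDA wording can be read as naming the instrument, and the parent-study sentence sits under repeated visits, so it points towards several recalls rather than one. That stands. What remains is that the plan names one recall before one visit and gives no rule for averaging or correction; following it as written yields a one-day DII.

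**All diet results are weakened.** This is too broad, for the reasons given in the working: the serum vitamin analyses are untouched and the group means of DII are not biased.

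**Repeats are ready to be averaged for everyone.** They are not. The parent protocol allows study portions, including questionnaires, to be dropped. Post-intervention recalls fall in the last week on oxytocin or placebo. Parent controls have no second phase and repeat the questionnaires only if they accept the acute dose. Averaging only where repeats exist would make the exposure more precise in pain participants than in controls, which is the contrast under study. This objection stands and shapes the fix.

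**A real association would probably be missed.** The figures do not support that as a general statement: one-recall power exceeds one half in four of the six cases tabulated and reaches 0.80 at the favourable end.

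Finally, PANDA is an ancillary, cross-sectional project that relies partly on stored data, and its recall is interviewer-led. Careful interviewing reduces reporting error but not real variation in diet from day to day.

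**Conclusion.** The concern holds in this form: a DII based on one day's intake, entered as an error-free continuous predictor, biases the regression coefficients for H1b, H1c and the regression form of H1a towards zero and lowers power.

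Under the assumed values, the slope is multiplied by 0.25 to 0.70 with one recall and by 0.40 to 0.82 with two. A second recall adds about 0.06 to 0.18 to power at n = 90. These gains require two usable recalls from every participant, which the stored data may not provide, so they are an upper limit on what the fix achieves. They also rest on classical error that is unrelated to the outcome, and on effect sizes and reliabilities that the documents do not give. The direction of the bias does not depend on the exact values; its size does.

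This is an improvement worth making to an ancillary aim. It does not touch the parent trial's comparison of oxytocin with placebo.

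**What to change.** 1. **New participants (40).** Write a 24-hour recall into each of the two scheduled sessions, and compute DII from mean intake over the two days.
2. **Stored knee OA participants.** Use the Phase One and Phase Two baseline recalls where both exist. Do not use the on-treatment recalls.
3. **Stored controls.** Keep the single recall where that is all there is.
4. **Analysis.** Estimate the within-study reliability of DII from the replicates. Report a regression-calibrated sensitivity analysis that allows for the number of recalls per person. State its assumption that within-person variance is similar across pain groups, since the replicates from stored data will come mainly from pain participants.
5. **Reporting.** Show the single-recall DII analysis alongside, because exposure precision will differ between stored controls and pain participants.

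Cost: one extra recall interview and its nutrient-database entry for 40 people, entry of any second baseline recalls not yet coded, and a short addition to the analysis section. No new visits are needed. The unequal precision is a real downside that calibration handles only as far as its variance assumption holds.
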